7.11.3 Vital Signs

Refer to [Appendix A](#) for scheduled vital signs measurement visits. Individual results for vital sign measurements that meet the Takeda predefined vital signs MAV criteria in [Appendix C](#) will be presented in a data listing. All vital sign data will be presented in the listings. Vital sign MAVs will be flagged in the listings.

7.11.4 12-Lead ECGs

The scheduled 12-lead ECG data will be collected according to [Appendix A](#), including baseline and the final visit. The ECG evaluations will be categorized as Normal; Abnormal, not clinically significant; and Abnormal, clinically significant. ECG results will be presented as a shift from baseline table and all ECG data will be presented in data listings.

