13. The subject has current or recent (within 6 months) gastrointestinal disease that would be expected to influence the absorption of drugs (ie, a history of malabsorption, esophageal reflux, peptic ulcer disease, erosive esophagitis, frequent [more than once per week] occurrence of heartburn, or any surgical intervention).
14. The subject has a non-standard diet (eg, vegetarian or vegan) or lifestyle (including nighttime work, extreme physical activity such as weights lifting), which may interfere with the trial.
15. The subject has a history of cancer, except basal cell carcinoma which has been in remission for at least 5 years prior to Day 1 of Period 1.
16. The subject has a positive test result for hepatitis B surface antigen (HBsAg), hepatitis C virus (HCV) antibody, human immunodeficiency virus (HIV) antibody or syphilis at Screening.
17. The subject has used nicotine-containing products (including but not limited to cigarettes, pipes, cigars, chewing tobacco, nicotine patch or nicotine gum) within 28 days prior to Check-in Day -1. Cotinine test is positive at Screening or Check-in (Day -1).
18. The subject has poor peripheral venous access.

19. The subject has donated or lost 450 mL or more of his or her blood volume (including plasmapheresis), or had a transfusion of any blood product within 30 days prior to Day 1 of Period 1.
20. The subject has abnormalities in routine physician examination, laboratory and/or ECG findings.
21. The subject has a systolic blood pressure >130 mm Hg or <100 mm Hg, diastolic blood pressure >90 mm Hg or <70 mm Hg; heart rate <60 beats per minute (bpm) or >80 bpm at Screening (Day -28 to Day -2) or Check-in to Period 1 (Day -1).
22. The subject has consumed caffeine or xanthine-containing food or drinks within 72 hours prior to Check-in (Day -1).
23. The subject has dehydration due to vomiting, diarrhea, or any other reason within 24 hours prior to study start.
24. The subject has drug intolerance.

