13.1.4 Subject Condition Assessments

Subject condition assessments will be performed using the Safety Set. All subject condition assessments, including AEs, clinical laboratory evaluations, 12-lead ECG results, and vital signs will be summarized with descriptive statistics, where appropriate, and presented in the data listings.

All AEs will be coded using MedDRA and presented in the data listings.

A postdose AE is defined as an AE that occurs after the subject receives the first dose of study medication and within 30 days after the last dose of study medication is received. Summary of AEs will include numbers and percentages of subjects experiencing AEs by system organ class and preferred term. AEs will also be summarized based on their intensity and relationship to study medication by system organ class and preferred term. If a subject has more than 1 AE that codes to the same preferred term, the subject will be counted only once for that preferred term within regimen. Similarly, if a subject has more than 1 AE within a system organ class category, the subject will be counted only once in the system organ class category within the regimen. In the intensity summary, a subject will be counted only in the highest intensity category for each preferred term and each organ class. In the relationship to study medication summary, a subject will be counted only in the highest relationship category for each preferred term and each system organ class. Each summary table will include incidences of adverse events for each regimen and overall.

All AE summary tables will be listed in the SAP.

AEs will be summarized using preferred term and primary system organ class.

Individual results for clinical hematology and serum chemistry laboratory tests that are outside of normal range and results that meet Takeda predefined criteria for markedly abnormal values will be considered as clinically significant and identified in summary tables, if applicable. Observed values and change from Baseline will be summarized by regimen. All laboratory values will be presented in the data listings.

Individual vital sign values that meet the Takeda predefined markedly abnormal criteria will be considered as clinically significant and identified in a summary table. The vital sign measurements at predefined time points and change from Baseline will be summarized by regimen. All vital signs data will be presented in the data listing.

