5.2 Additional Endpoints

- CCI [REDACTED]
- Percentage of subjects who experience at least 1 postdose AE.
- Percentage of subjects who have clinically significant changes in laboratory tests at least once postdose.
- Percentage of subjects who have clinically significant changes in vital sign measurements at least once postdose.
- Percentage of subjects who have clinically significant changes in electrocardiogram (ECG) parameters at least once postdose.
- Percentage of subjects who experience at least 1 postdose event of hypoglycemia.

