7.1.1 Study Definitions

Generally, Baseline is defined as the value or observation prior to first dose of study drug, i.e. Day 1 Period 1. Where applicable, pre-dose values will be obtained for each dosing Period.

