Appendix A Study Procedures

| Study Day: | Days -28 to -2 (b) | Drug Intake Periods 1 through 4 (a) | | | | | Study Exit (Day 4 of Period 4)/ Early Termination Visit | Follow-up Phone Call (d) |
|---|--------------------------|-------------------------------------|--------------|-------|-------|---------------------------------------|--|--------------------------------|
| | | Day -1 (Check- in) | Day 1 (c) | Day 2 | Day 3 | Day 4 (Period s 1, 2, and 3) | | |
| Informed consent | X | | | | | | | |
| Inclusion/exclusion criteria | X | X | | | | | | |
| Demographics and medical history | X | | | | | | | |
| Medication history | X | | | | | | | |
| Physical examination | X | X | | | | | X | |
| Vital signs (e) | X | X | X | | | X | X | |
| Height, weight and BMI | X | | | | | | | |
| Concomitant medications | X | X | X | X | X | X | X | X |
| 12-lead ECG (f) | X | X | | | | | X | |
| Clinical laboratory evaluations (g) | X | | X (h) | | | | X | |
| Urine drug, cotinine, and alcohol breath screen | X | X | | | X | X | X | |
| Urine pregnancy test (hCG) (i) | X | X | | | | | X | |
| HBsAg, Anti-HCV, HIV, and syphilis (i) | X | | | | | | | |
| Confinement | | X | X (j) | X (j) | | | | |
| Study drug dosing (k) | | | X | | | | | |
| PK blood collection (l) | | | X | X | X | X | X | |
| Predose/AE assessment (m) | X | X | X | X | X | X | X | X |

(a) There will be at least 7 days between the dose in 1 period and the dose in a subsequent period.

- (b) Screening may consist of 1 or more visits. Subjects will sign an informed consent form at the first visit and return to the clinic in a fasted state for safety laboratory testing at the second visit. Screening procedures must be performed within 28 days prior to administration of investigational product.
- (c) Day 1 of each drug intake period.
- (d) Follow-up phone call will be made 14 ± 2 days after study exit to inquire about any AE or SAEs, and concomitant medications taken since final dose. Any AE/SAE spontaneously reported within 30 days postdose will be included within the database as AEs.
- (e) Vital signs: oral body temperature, sitting blood pressure (after resting 5 minutes), respiratory rate, and pulse (beats per minute). Vital signs will be measured just prior to dosing on Day 1 of periods 1 through 4. When vital signs are scheduled at the same time as blood draws, the blood draw will take priority and vital signs will be obtained within 0.5 hour before or after the scheduled blood draw.

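### SAP 7.11.3 plans only listings for vital signs, so the retained percentage endpoint and the protocol's by-regimen change summary have no planned output and no suitable baseline

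*SAP*

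**What the plan says.** Protocol 13.1.4 asks for two vital-sign outputs. The first concerns outlying values: "Individual vital sign values that meet the Takeda predefined markedly abnormal criteria will be considered as clinically significant and identified in a summary table". The second is a descriptive summary: "The vital sign measurements at predefined time points and change from Baseline will be summarized by regimen".

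SAP 5.2 lists as an endpoint "Percentage of subjects who have clinically significant changes in vital sign measurements at least once postdose"; Protocol 5.2.2.2 lists the same one.

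SAP 7.11.3 then plans a listing of values meeting the Appendix C criteria, a full listing ("All vital sign data will be presented in the listings") and flags ("Vital sign MAVs will be flagged in the listings"). It names no table, no count or percentage, no descriptive statistic and no change from baseline.

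On the reference value, SAP 7.1.1 states as a general rule that "Baseline is defined as the value or observation prior to first dose of study drug, i.e. Day 1 Period 1". It adds that predose values are obtained in each period where applicable, but does not make them the reference for change. The schedule in SAP Appendix A provides such a value ("Vital signs will be measured just prior to dosing on Day 1 of periods 1 through 4"), together with readings at each check-in and on Day 4 of every period, which in Period 4 is the Study Exit visit.

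**The concern.** Programmers work from the SAP. If they follow 7.11.3 as it stands, one of the five subject-condition endpoints gets no numerator, denominator or regimen grouping, and a summary that the protocol requires is not produced.

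The gap is confined to vital signs. Laboratory data get change from baseline and n (%) of markedly abnormal values (SAP 7.11.2), ECGs get a shift table (7.11.4), and adverse events get tables by regimen (7.11.1). Yet vital signs are the one assessment of laboratory tests, ECG and vital signs that is scheduled before and after the dose in all four periods, so a within-period summary is possible for every regimen.

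If someone restores the change summary without further thought, the default Baseline in 7.1.1 applies. A change labelled as belonging to one regimen would then usually run across other regimens as well.

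**Working it through.** The plan gives no figure to reproduce here. The check is a comparison of texts, followed by a count from the design.

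**1. Required against planned**

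| Output | Protocol 13.1.4 / endpoint list | SAP 7.11.3 |
|---|---|---|
| Markedly abnormal values | Summary table | Listing and flags |
| Percentage of subjects with a clinically significant change | Endpoint (Protocol 5.2.2.2, SAP 5.2) | None |
| Observed values by time point and regimen | Summary | Listing |
| Change from Baseline by regimen | Summary | None |

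**2. What a Period 1 Baseline would span**

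Inputs: 72 subjects, 18 per sequence; sequences ABCD, BCDA, CDAB and DABC; doses 7 days apart (SAP 4.4 and Figure 1). All 72 are assumed to complete.

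Each regimen appears once in each period, with 18 subjects per cell. For any regimen:

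- Given in Period 1: 18 subjects, 0 earlier doses.
- Given in Period 2: 18 subjects, 1 earlier dose, Baseline 7 days before that period's dose.
- Given in Period 3: 18 subjects, 2 earlier doses, 14 days.
- Given in Period 4: 18 subjects, 3 earlier doses, 21 days.

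Changes that span at least one earlier dose: 18 + 18 + 18 = 54, and 54/72 = 75%. With the same-period Day 1 predose value as reference, the count is 0 of 72.

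**3. What this does to the estimates**

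Let B be a subject's Period 1 Baseline and Y_A, Y_B the Day 4 values under two regimens. Then

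(Y_A − B) − (Y_B − B) = Y_A − Y_B,

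so the shared Baseline cancels in a within-subject difference. Let d_p be the mean drift from Baseline to period p. Each regimen's mean change then contains (18d_1 + 18d_2 + 18d_3 + 18d_4)/72 = (d_1 + d_2 + d_3 + d_4)/4, the same quantity for A, B, C and D. Drift is therefore added to each regimen's own change but drops out of the comparisons, provided that the cells stay at 18.

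**4. Which readings belong to which regimen**

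SAP 7.11.1 attributes an adverse event to the regimen last dosed, until just before the next dose. Under the same rule, a regimen given in Periods 1 to 3 has two scheduled postdose readings: Day 4, and the next check-in on about Day 7. In Period 4 it has one, at Study Exit. Each regimen thus has 54 subjects with two readings and 18 with one, so the opportunity to be flagged is equal across regimens when data are complete.

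**5. Appendix C limits against the entry range**

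The title of Appendix C speaks of changes from Baseline, but its criteria are absolute values. Protocol 7.2 sets the entry range (for systolic pressure, "The subject has a systolic blood pressure >130 mm Hg or <100 mm Hg" excludes). Distances from the entry limits to the flags:

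- Systolic: high 180 − 130 = 50 mm Hg; low 100 − 85 = 15 mm Hg.
- Diastolic: high 110 − 90 = 20 mm Hg; low 70 − 50 = 20 mm Hg.
- Pulse: high 120 − 80 = 40 bpm; low 60 − 50 = 10 bpm.

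**The case against.** The strongest reply is that nothing is lost. Every value is listed, every markedly abnormal value is flagged, SAP 5.2 still names the endpoint, SAP 7.1 says that categorical data are tabulated as counts and percentages, and SAP 7.11 summarises safety data by study arm unless told otherwise. It is true that the percentage could be counted by hand. But the general text names no vital-sign table, time point or baseline, study arm is undefined in a crossover where the protocol speaks of regimen, and the specific section gives listings.

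The baseline argument concerns an analysis that SAP 7.11.3 does not contain, and 7.1.1 presents Period 1 only as the general rule. Both points stand. The Baseline is a default, and it matters once the protocol's summary is restored. The protocol does not require a same-period baseline, so that choice is a preference, though a well-supported one.

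A reader might infer three stronger things that the documents do not support:

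- That by-regimen comparisons could not isolate the regimen. Step 3 shows that they can with complete data. Drug carryover should also be small, because Protocol 6.2 puts the 7-day washout above five half-lives of either drug.
- That the flagged listings will be almost empty. The upper systolic and pulse limits are distant, but the low flags lie only 10 bpm and 15 mm Hg beyond the entry limits, and no document gives an expected flag rate.
- That SAP 7.13 declares no departure from the protocol. Its heading concerns changes to the SAP, so its entry of not applicable cannot carry that meaning.

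**Conclusion.** The mismatch is confirmed. The protocol requires two descriptive vital-sign outputs and both documents keep the percentage endpoint, but the SAP plans neither output. This should be corrected, although it concerns descriptive safety reporting only and leaves the primary bioequivalence analysis untouched.

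The baseline matter is secondary. Under the default, 75% of each regimen's changes would span other regimens, and the effect is mainly common drift in each regimen's own mean change. The count assumes that all 72 subjects complete; with the planned 14% drop-out (72 × 0.86 = 61.92, about 62 completers) the balance that cancels drift between regimens may hold only approximately. The within-period change is also sparse: it compares a predose reading with one about 72 hours later, so it will not show effects near peak concentration.

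**What to change.** In SAP 7.11.3 add two tables:

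1. Number and percentage of subjects with at least one postdose value meeting Appendix C, by regimen and overall. Attribute readings taken after a dose and before the next dose to the regimen dosed, as SAP 7.11.1 does for adverse events. This covers the check-in readings of Periods 2 to 4. The Day 1 predose reading of the next period serves only as that period's baseline.
2. Observed values, and change from the same period's Day 1 predose value to Day 4, by regimen.

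In SAP 7.1.1, state that the vital-sign baseline is the same-period predose value. Reconcile the title of Appendix C with its absolute limits. If the sponsor prefers listings only, the SAP should state and justify the departure from Protocol 13.1.4 and say how the endpoint in 5.2 will be reported.

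The cost is SAP wording and two descriptive tables. No new data or visits are needed.

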7.11.5 Other Observations Related to Safety

Physical examination findings will be presented in data listings. No summary tables will be provided.

All cases of overdose will be listed.

Follow-up phone call information will be listed.

7.12 Interim Analysis

Not applicable.

7.13 Changes in the Statistical Analysis Plan

Not applicable.

Appendix A Study Procedures

| Study Day: | Days -28 to -2 (b) | Drug Intake Periods 1 through 4 (a) | | | | | Study Exit (Day 4 of Period 4)/ Early Termination Visit | Follow-up Phone Call (d) |
|---|--------------------------|-------------------------------------|--------------|-------|-------|---------------------------------------|--|--------------------------------|
| | | Day -1 (Check- in) | Day 1 (c) | Day 2 | Day 3 | Day 4 (Period s 1, 2, and 3) | | |
| Informed consent | X | | | | | | | |
| Inclusion/exclusion criteria | X | X | | | | | | |
| Demographics and medical history | X | | | | | | | |
| Medication history | X | | | | | | | |
| Physical examination | X | X | | | | | X | |
| Vital signs (e) | X | X | X | | | X | X | |
| Height, weight and BMI | X | | | | | | | |
| Concomitant medications | X | X | X | X | X | X | X | X |
| 12-lead ECG (f) | X | X | | | | | X | |
| Clinical laboratory evaluations (g) | X | | X (h) | | | | X | |
| Urine drug, cotinine, and alcohol breath screen | X | X | | | X | X | X | |
| Urine pregnancy test (hCG) (i) | X | X | | | | | X | |
| HBsAg, Anti-HCV, HIV, and syphilis (i) | X | | | | | | | |
| Confinement | | X | X (j) | X (j) | | | | |
| Study drug dosing (k) | | | X | | | | | |
| PK blood collection (l) | | | X | X | X | X | X | |
| Predose/AE assessment (m) | X | X | X | X | X | X | X | X |

(a) There will be at least 7 days between the dose in 1 period and the dose in a subsequent period.

- (b) Screening may consist of 1 or more visits. Subjects will sign an informed consent form at the first visit and return to the clinic in a fasted state for safety laboratory testing at the second visit. Screening procedures must be performed within 28 days prior to administration of investigational product.
- (c) Day 1 of each drug intake period.
- (d) Follow-up phone call will be made 14 ± 2 days after study exit to inquire about any AE or SAEs, and concomitant medications taken since final dose. Any AE/SAE spontaneously reported within 30 days postdose will be included within the database as AEs.
- (e) Vital signs: oral body temperature, sitting blood pressure (after resting 5 minutes), respiratory rate, and pulse (beats per minute). Vital signs will be measured just prior to dosing on Day 1 of periods 1 through 4. When vital signs are scheduled at the same time as blood draws, the blood draw will take priority and vital signs will be obtained within 0.5 hour before or after the scheduled blood draw.
- (f) ECG performed at Screening, Check-in (Day -1 of Period 1), and Study Exit Day 4 of Period 4, or if a subject terminates early from the study.
- (g) Hematology, serum chemistries, and urinalysis tests will be done at a local laboratory.
- (h) Predose hematology, serum chemistries, and urinalysis tests will be done for Period 1 only.
- (i) A urine pregnancy test and HBsAg, Anti-HCV, HIV, and syphilis tests will be done locally.
- (j) Following the 24-hour blood sample collection on Day 2 of each period, subjects will be discharged from the clinic and will return to the clinic for the 36-hour blood sample collection on Day 2 and on Days 3 and 4 of each period to complete study procedures.
- (k) Study drug will be administered on Day 1 of each period at 08:00 (± 1) hours, following an 8- hour fast. Dosing may be staggered to help facilitate logistics at the site.
- (l) Blood samples for PK obtained predose (within 15 minutes prior to dose), 0.25, 0.5, 1, 1.5, 2, 3, 4, 6, 8, 12, 16, 24, 36, 48, and 72 hours postdose. The PK sample should not be collected at the Early Termination Visit if a PK collection is not scheduled.
- (m) Predose AEs will be captured immediately following the signing of the informed consent at Screening until dosing on Day 1 of Period 1. The routine collection of AEs will continue through to the follow-up phone call.

Appendix B Criteria for Identification of Markedly Abnormal Laboratory Values

Hematology—Criteria for Markedly Abnormal Values

| Parameter | Unit | Low Abnormal | High Abnormal |
|----------------|--------------|--------------------------------|---------------------------------|
| Hemoglobin | Both | $< 0.8 \times \text{LLN}$ | $> 1.2 \times \text{ULN}$ |
| Hematocrit | Both | $< 0.8 \times \text{LLN}$ | $> 1.2 \times \text{ULN}$ |
| RBC count | Both | $< 0.8 \times \text{LLN}$ | $> 1.2 \times \text{ULN}$ |
| WBC count | Both | $< 0.5 \times \text{LLN}$ | $> 1.5 \times \text{ULN}$ |
| Platelet count | Conventional | $< 75 \times 10^3/\mu\text{L}$ | $> 600 \times 10^3/\mu\text{L}$ |
| | SI | $< 75 \times 10^9/\text{L}$ | $> 600 \times 10^9/\text{L}$ |

LLN= lower limit of normal, RBC= red blood cell, ULN= upper limit of normal, WBC= white blood cell.

Serum Chemistry—Criteria for Markedly Abnormal Values

| Parameter | Unit | Low Abnormal | High Abnormal |
|----------------------|--------------|---------------------------|---------------------------|
| ALT | Both | -- | $> 3 \times \text{ULN}$ |
| AST | Both | -- | $> 3 \times \text{ULN}$ |
| Alkaline phosphatase | Both | -- | $> 3 \times \text{ULN}$ |
| Total bilirubin | Conventional | -- | $> 2.0 \text{ mg/dL}$ |
| | SI | -- | $> 34.2 \mu\text{mol/L}$ |
| GGT | Both | -- | $> 3 \times \text{ULN}$ |
| Albumin | Conventional | $< 2.5 \text{ g/dL}$ | -- |
| | SI | $< 25 \text{ g/L}$ | -- |
| Total protein | Both | $< 0.8 \times \text{LLN}$ | $> 1.2 \times \text{ULN}$ |
| Creatinine | Conventional | -- | $> 2.0 \text{ mg/dL}$ |
| | SI | -- | $> 177 \mu\text{mol/L}$ |
| Blood urea nitrogen | Conventional | -- | $> 30 \text{ mg/dL}$ |
| | SI | -- | $> 10.7 \text{ mmol/L}$ |
| Sodium | Conventional | $< 130 \text{ mEq/L}$ | $> 150 \text{ mEq/L}$ |
| | SI | $< 130 \text{ mmol/L}$ | $> 150 \text{ mmol/L}$ |
| Potassium | Conventional | $< 3.0 \text{ mEq/L}$ | $> 6.0 \text{ mEq/L}$ |
| | SI | $< 3.0 \text{ mmol/L}$ | $> 6.0 \text{ mmol/L}$ |
| CPK | Both | -- | $> 5 \times \text{ULN}$ |

ALT= alanine aminotransferase, AST= aspartate aminotransferase, GGT= γ -glutamyl transferase, CPK= creatine phosphokinase, LLN= lower limit of normal, ULN= upper limit of normal.

Appendix C Criteria for Abnormal Changes from Baseline of Vital Signs

| Parameter | Unit | Lower Criteria | Upper Criteria |
|--------------------------|-------------|-----------------------|-----------------------|
| Pulse | bpm | <50 | >120 |
| Systolic blood pressure | mm Hg | <85 | >180 |
| Diastolic blood pressure | mm Hg | <50 | >110 |
| Body temperature | °C | < 35.6 | >37.7 |

ELECTRONIC SIGNATURES

| Signed by | Meaning of Signature | Server Date (dd-MMM-yyyy HH:mm 'UTC') |
|-----------|--------------------------------|--|
| PPD | Statistical Approval | 20-Jun-2018 14:26 UTC |
| | Pharmacovigilance Approval | 20-Jun-2018 14:28 UTC |
| | Biostatistics Approval | 20-Jun-2018 14:40 UTC |
| | Clinical Pharmacology Approval | 27-Jun-2018 21:27 UTC |
| | Clinical Science Approval | 03-Jul-2018 19:48 UTC |
